# EFFECTIVENESS OF ULTRASONOGRAPHY IN THE EVALUATION OF DIFFICULT AIRWAY IN OBESE PATIENTS

## INTRODUCTION

Obesity has become an increasing public health problem worldwide. Obesity-related changes in pulmonary mechanics and metabolic, cardiovascular and respiratory physiology increases the risk of mortality and morbidity in the perioperative period.

Obesity is a proinflammatory multisystemic disease defined as hypertrophy and/or hyperplasia of adipose tissue. Genetic characteristics, endocrine disorders, neurological, psychological and environmental factors are effective in the development of obesity. Obesity is classified according to body mass index. Body Mass Index (BMI) is defined as the ratio of body weight in kilograms (kg) to the square of height in meters (m). According to the World Health Organization (WHO), obesity is a global epidemiological epidemic and there are 1.5 billion obese patients worldwide.

Obesity is a main factor causing difficulties in airway management. Difficult airway is characterized by difficult mask ventilation and difficult intubation. It is more frequent in obese patients, because the neck is short and thick, and the larynx is displaced anteriorly and upwards. The amount of pharyngeal and palatal soft tissue is increased and the tongue is enlarged. Difficulty should be expected in providing airway management such as mask ventilation, direct laryngoscopy and tracheostomy, as a result of the enlargement of the face, neck, chest and abdomen circumferences with a high Mallampati score. The incidence of difficult intubation in patients with BMI > 35 kg/m^2 has been reported as 15.5%. But the literature also states that difficulty in intubation is not related to BMI but due to large neck diameter and mallampati score III-IV. The probability of difficult intubation was 5% in those with a neck circumference of 40 cm and 35% in those with a neck circumference of 60 cm^5. Indicators of difficult intubation in the pre-operative assessment are small oral cavity, short neck, limited head and neck movements due to increased fat tissue, mallampati score 3 or higher, sternomental distance of 12.5 cm or thyromental distance of less than 6 cm^6.

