Ultrasonography is a low-cost, safe and rapid evaluation method. Some studies show that the measurement of soft tissue thickness in the anterior neck at the level of the vocal cords plays an important role in predicting difficult laryngoscopy in obese patients. Airway evaluation with ultrasonography can be performed in emergency departments, intensive care units and operating rooms. In addition to the upper airway evaluation, the lower airway, lungs and pleura can also be evaluated. Again, difficult intubation is envisaged in patients with pretracheal soft tissue thickness of 28 mm and neck circumference of more than 50 cm at the level of the vocal cord.

In this study, it is aimed to determine the correlation between ultrasonographic measurements (anterior cervical soft tissue thickness at the level of the skin-anterior vocal cord junction, the distances between skin-hyoid bone, skin-thyrohyoid membrane, skin-midpoint of

the epiglottis) and difficult mask ventilation (Han Scale) and difficult laryngoscopy (Cormack-Lehane Classification) in obese patients ( $BMI \geq 30 \text{ kg/m}^2$ ).

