## METHODS AND MATERIALS

A total of 150 patients ages between 18-80 years,  $BMI \geq 30 \text{ kg/m}^2$ , ASA I-III who will undergo elective surgery under general anesthesia will be included in the study. Patients with facial and cervical trauma or cancer surgery, tracheostomy or thyroid surgery, non-cooperative patients and pregnant women will be excluded.

During the pre-operative evaluation gender, age, height, weight, type of surgery, BMI, neck circumference and extension, thyromental distance, sternomental distance, hyomental distance, mouth opening and distance between incisors will be measured to evaluate the dentition. ASA physical status will be recorded. OSAS will be evaluated based on Apnea-Hypopnea Index (AHI) ( $AHI < 5$  simple snoring,  $5 \leq AHI < 15$  Mild OSAS,  $15 \leq AHI < 30$  Moderate OSAS,  $AHI \geq 30$  Severe OSAS). Modified Mallampati Score will be recorded. During this test, the pharyngeal structures will be evaluated by having the patient open his/her mouth as much as possible and protrude his/her tongue forward as much as possible in the neutral position without making a sound. (Class I: uvula, soft palate, tonsil bed, anterior and posterior plicae can be easily seen. Class II: uvula and soft palate can be seen. Class III: soft palate and base of the uvula are visible. Class IV: the uvula is completely covered by the tongue root and the pharyngeal wall cannot be seen). Patients will have an upper lip bite test. In order to perform the upper lip bite test, the patients will be asked to bite their upper lip with their lower incisors. According to this test; if the patient can bite the upper lip above the vermilion with the lower incisors, he/she will be evaluated as class 1; if the patient can bite the upper lip below the vermilion with the lower incisors, he/she will be evaluated as class 2; if the patient cannot bite the upper lip with the lower incisors, he/she will be evaluated as class 3. In accordance with the original study, class 1 and 2 will be considered as easy and class 3 as difficult intubation criteria.

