Ultrasonographic measurements will be performed by the main researcher anesthesiologist with the patient in supine position with head and neck placed neutrally. Anterior cervical soft tissue measurement will be performed in the transverse plane with a 13-6 MHz linear USG probe (Sonosite M-Turbo), including the hyoid bone, thyrohyoid membrane and anterior vocal cord junction. At the level of the hyoid bone, the minimum distance between the hyoid bone and skin (HCM) will be measured and recorded; at the level of the thyrohyoid membrane, the distance between the epiglottis midpoint and skin (ECM) between the hyoid bone and thyroid cartilage; and at the level of the vocal cord, the distance between the vocal cord anterior junction and skin (VCM) will be measured and recorded.

Train of four (TOF) monitoring will be applied to all patients along with standard anesthesia monitoring. Standard induction of anesthesia, 2 mg/kg propofol, 2 mcg/kg fentanyl, 0.6 mg/kg rocuronium as standard to be done intravenously. Mask ventilation will be done with a disposable plastic mask. The Han Scale will be used to assess difficult mask ventilation. (Class 1- Easy mask ventilation, Class 2- Oral airway / adjuvant requirement with/without NMBA,

Class 3- Inadequate, difficult and unstable two practitioners with/without NMBA, Class 4- Impossible with/without NMBA ventilation) The laryngoscopy procedure will be performed by an anesthesiologist who has a minimum of 2 years of anesthesia experience and does not know about USG measurements, with an appropriate size Macintosh blade, after adequate muscle relaxation. The laryngoscopy image will be evaluated with the Cormack-Lehane classification. (Class 1- Glottis fully visible, Class 2- a. Glottis partially visible b. Only arytenoid cartilages visible, Class 3- Only epiglottis visible, Class 4- Epiglottis or glottis not visible) Han Scale 3-4 difficult mask ventilation, Cormack-Lehane 2b-4 will be considered difficult laryngoscopy.

[figure not shown]

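### Does the yes/no definition of difficult airway throw away information that the correlation in the aim needs?

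*Protocol*

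**What the plan says.** The aim, at the end of the Introduction, reads "it is aimed to determine the correlation between ultrasonographic measurements" and then names the outcomes as "difficult mask ventilation (Han Scale) and difficult laryngoscopy (Cormack-Lehane Classification) in obese patients". Each outcome is called difficult, and each is followed by its full scale.

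Methods and Materials describes the two assessments. For ventilation, "The Han Scale will be used to assess difficult mask ventilation", with four ordered classes. For laryngoscopy, "The laryngoscopy image will be evaluated with the Cormack-Lehane classification", with five ordered classes (1, 2a, 2b, 3, 4). The section closes with the cut-points: "Han Scale 3-4 difficult mask ventilation, Cormack-Lehane 2b-4 will be considered difficult laryngoscopy".

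The same section sets the size: "A total of 150 patients ages between 18-80 years". The protocol names no correlation coefficient, model or test, and gives no expected grade distribution or rate for either outcome. The nearest figure is in the Introduction, where the incidence of difficult intubation at BMI above 35 "has been reported as 15.5"%. That is a different endpoint in a narrower population.

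**The concern.** Taken strictly, the defined terms make the aim a correlation between a continuous distance and a binary variable. Dichotomising an ordered scale ignores the order within the easy group (Han 1 and 2; Cormack-Lehane 1 and 2a) and within the difficult group. When few patients are difficult, most of the sample falls into one undifferentiated category: at 15.5%, 150 × 0.155 ≈ 23 patients would be difficult and 127 easy. If the distance rises steadily across all grades, discarding that order lowers the power of the only stated aim, while the finer grades would cost nothing extra to use. Two possible readings of the outcome would also leave room to choose between analyses after the grades are seen.

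**Working it through.** **1. What the text commits to.** The aim attaches the whole scale to each outcome; Methods grades on the whole scale and then says which grades count as difficult. Nowhere does the protocol say that the correlation uses the split or that the grades are set aside. Correlating the distance with the grade and classifying difficulty by the cut-point are compatible, and the text allows both. A loss can therefore be charged only to an analysis that the protocol does not specify.

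**2. Size of the loss if the split were used.** There is no figure in the plan to reproduce. All inputs below are assumptions: difficult share q = 15.5% (borrowed from the Introduction as an example), and the grade distributions.

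Proportional odds, small effects: information ∝ 1 − Σp³.
- Split: 1 − 0.845³ − 0.155³ = 3 × 0.155 × 0.845 = 0.393.
- Cormack-Lehane 50/34.5/8/6/1.5%: 1 − (0.1250 + 0.0411 + 0.0005 + 0.0002 + 0.0000) = 0.833. Loss = 1 − 0.393/0.833 = 53%.
- Han 80/4.5/14.5/1%: 1 − (0.5120 + 0.0001 + 0.0030 + 0.0000) = 0.485. Loss = 1 − 0.393/0.485 = 19%.

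Latent normal: information = Σ p × (mean latent score in the class)².
- Split: the cut is at 1.015, where the density is 0.238, so 0.238²/(0.155 × 0.845) = 0.43.
- The same Cormack-Lehane distribution: 0.785. Loss = 45%.
- The same Han distribution: 0.516. Loss = 16%.

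So the range is about 16–45% under one model and 19–54% under the other, the 54% arising when the easy patients divide about evenly over two grades. A span of 16–54% mixes the two models.

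**3. Is the lower end a floor?** No. It comes from stopping at 80% in class 1. With Cormack-Lehane 84/0.5/8/6/1.5%, the proportional-odds information is 0.407 and the loss 1 − 0.393/0.407 = 3%; the latent-normal loss is 7%.

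**4. Does the direction hold?** Both formulas assume one common effect across every grade boundary. Simulated power at N = 150, two-sided 5%, 15.5% difficult, over the assumed grade distributions:

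| Assumed truth | Yes/no split | Spearman on full grade |
|---|---|---|
| Gradient across all grades, latent correlation 0.25 | 50–53% | 57–75% |
| Distance shifted 0.5 SD in difficult patients only | 58–60% | 30–48% |
| Distance shifted 0.6 SD in difficult patients only | 73–77% | 40–64% |

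In the last two rows there is no gradient among easy grades. Ranking easy patients against each other then adds noise, and the full-grade analysis is the one more likely to miss the association. Nothing in the protocol says which truth applies.

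**5. Do the cut-points fit the question?** The title and Introduction are about predicting a difficult airway, which is a yes/no target. Fixing its threshold beforehand prevents a choice of cut-point after the data are seen.

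**The case for a change.** The strongest reply is that choosing a coefficient may be left to an analysis plan, but what the outcome variable is belongs in the protocol, and here the protocol defines its own terms as binary. If distance does rise smoothly across grades, the loss is real: at a latent correlation of 0.25 the full grade gains between a few and roughly 25 percentage points of power. One added sentence would settle the matter at no cost in data.

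Part of this stands. The wording is ambiguous, and the loss figures are arithmetically right under their models. But an ambiguity in which one reading keeps the grades is not a plan to discard them, and whether a named scale enters as a grade or as a cut is a detail that an analysis plan commonly settles. Using the full grade is also not free: when the difference lies only in difficult patients, it costs about 10 to 30 points of power, as the 0.5 SD row of the table shows (58 − 48 = 10; 60 − 30 = 30). Which analysis is better depends on an unknown pattern, and reasonable statisticians would differ on it.

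**Conclusion.** The concern does not hold. The protocol does not commit the correlation to the yes/no outcome, and its pre-set cut-points suit the question of predicting a difficult airway. The possible loss ranges from about 3% of the grade information to about 54% at an assumed 15.5% difficult, depending on a grade distribution and a common-effect model that the protocol does not supply; the 15.5% itself belongs to difficult intubation at BMI above 35. Under another plausible pattern the ordering of power reverses. What is left is a wording detail that the unseen analysis plan may already settle, so no change to the protocol is called for on this ground.

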### MALLAMPATI CLASSIFICATION

Class I: Anterior and posterior pleats, soft palate, tonsil bed and uvula are seen as comfortable,

Class II: Uvula and soft palate are visible,

Class III: The soft palate and base of the uvula are visible,

Class IV: Uvula is completely covered by the tongue root, the pharyngeal wall is not visible.

### CORMACK-LEHANE CLASSIFICATION

[figure not shown]
1- Glottis fully visible

2 a. Glottis appear partially

b. Only arytenoid cartilages are visible

3- Only the epiglottis is visible

4- Epiglottis or glottis not visible

[figure not shown]

### UPPER LIP BITING TEST

If he can bite his upper lip above the vermilion with his lower incisors

If he can bite his upper lip under the vermilion with his lower incisors

Class 3- If he cannot bite his upper lip with his lower incisors

### APNE-HYPOPNEA INDEX

- $AHI < 5$  simple snoring,
- $5 \geq AHI < 15$  Mild OSAS,
- $15 \geq AHI < 30$  Moderate OSAS,
- $AHI \geq 30$  Severe OSAS

